## 6.2 Potential Benefits

There are two major potential benefits. Women taking part in the study may well improve their sleep, which in turn can improve their emotional and physical health. Those randomized to a program they do not like will be able to take the program, at no cost, that they think they will prefer after completing their assigned treatment.

The second benefit is to Black women in general who have insomnia. The effectiveness of SHUTi has not been established in Black women. This study will establish whether SHUTi, or SHUTi-BWHS (which are cognitive behavioral treatments for insomnia (CBTi), or both, are better at treating insomnia in Black women than usual care, which is giving the person sleep information. Since there are very few trained practitioners in CBTi, very few individuals get this most effective treatment for insomnia. Demonstration that online SHUTi or SHUTi-BWHS are effective will provide an impetus to make an online CBTi sleep treatment program accessible to Black women.

## 6.3 Analysis of Risks in Relation to Benefits

The risk/benefit ratio is highly favorable. Confidentiality is protected by the use of numbers to identify data; the protection of computer files by firewalls and limiting access to study personnel; the storage of consents in locked files; the statistical analysis of de-identified data; and the presentation of results of aggregate data. The benefit to scientific knowledge is large and far outweighs any risk.

## 7 Study Subject Selection

### 7.1 Subject Inclusion Criteria

In order to be eligible to participate in this study, an individual must meet all of the following criteria:

- Participants in the Black Women's Health Study (H-31535)
- BWHS participants with clinically elevated symptoms of insomnia previously reported on the 2015 BWHS questionnaire
- Internet access
- Access to computer or tablet

### 7.2 Subject Exclusion Criteria

An individual who meets any of the following criteria will be excluded from participation in this study:

- Self-reported unstable or acute medical condition, or condition requiring surgery in the next two months
- Self-reported untreated, current, and/or severe psychiatric condition
- Self-reported night shift work or alternating shift work employment
- Employed in a position where sleep restriction may endanger others' lives
- Self-reported 1 or more sleep disorders other than insomnia, such as sleep apnea, that are not being managed by a medically prescribed method.
- Intention to change use pattern of prescribed or over-the-counter sleep aid
- Consume 14 or more alcoholic drinks/week

## 8 Study Intervention

The study interventions will be determined by the treatment arm to which the participant is randomized and are summarized below.

- 1) Patient education (website providing sleep hygiene information) In this active control arm randomized participants will receive 'usual care' which will include internet-delivered patient education materials about sleep. The PE website focuses on symptoms of insomnia, the impact, prevalence, and causes of insomnia, considerations on when to see a doctor, and basic lifestyle, environmental, and behavioral strategies to improve sleep.
- 2) Standard SHUTi six-module program- SHUTi. This is an automated intervention that will be delivered over six sessions/modules, each lasting approximately 45-60 minutes. SHUTi tailors content based upon each participant's reported baseline sleep function, treatment adherence, and sleep progress. It incorporates all core elements of cognitive-behavioral therapy for insomnia (CBT-I).
- 3) SHUTi-BWHS (modified SHUTi six-module program tailored for Black women) We will develop this tailored version of SHUTi over a course of one year. The development will include an iterative process between the study investigators and key stakeholders such as Black women with a history of insomnia, a BWHS participant, a sleep physician from a medical center which serves a diverse patient population, and sleep researchers.

## 9 Study Procedures

Eligible subjects will be BWHS participants who completed a 7-question questionnaire about sleep, called the Insomnia Severity Index (ISI), which was included in the 2015 BWHS biennial follow-up questionnaire. The ISI was scored, with a score of 15 or more indicating symptoms of clinical insomnia disorder. Women with scores of 15 or more will be sent a brochure and email that will inform them of the opportunity to participate in a free program designed to test which of three insomnia treatments works best in Black women. Women will be selected at random since there are many more potentially eligible women (4000+) than women who can participate in the trial (n ~303). We will start with a group of 300 women selected at random from the potentially eligible subjects. The women will be directed to a special BWHS insomnia study website that contains the information in the brochure as well as an online screening questionnaire. Up to 6 reminders will be sent to the women to encourage participation. Once this group has been contacted and received a reminder, we will proceed to select a second group of 300 women at random. This procedure will be followed until the final group of 303 participants has been entered into the study.

After a woman submits her screening questionnaire (attached to this IRB application as "Eligibility Questionnaire"), an assessment will be made by the project coordinator to determine if she is eligible (e.g., does not have untreated sleep apnea). Those determined to be ineligible will be sent a thank you email and informed that they were not eligible for this trial. Those who meet the qualifications for the study will be contacted by the project coordinator to set up a telephone call to discuss the study and the informed consent. The coordinator will then call the woman; during the call the coordinator will review each section of the consent form. The consent form will contain a description of the study and describe all aspects of the study. Subjects will have ample time to consider whether or not they want to participate in the study. A verbal acknowledgement of consent, or non-consent, will be recorded in the study and a copy of the consent sent to the participant. A waiver of documentation of consent will be obtained from the IRB.

At this point, the BWHS Project Coordinator will enroll participants by entering their email and study ID into the SHUTi Administrative site. The BWHS Project Coordinator will be responsible for SHUTi program administration during the clinical trial. The SHUTi program will maintain contact with the woman through regular emails until the end of the woman's participation, as described below. Participants needing help will contact BWHS via email ([contact]) or the BWHS toll free number [contact]) posted on the SHUTi website. At the end of each woman's participation, the data she has supplied (ISI scores, etc.) will be transferred from the SHUTi database to BWHS. None of the data collected will have identifiers such as names and addresses.

Once a participant is enrolled, she will be sent a Welcome email with instructions for setting her password. Enrolled participants will login and complete an online Questionnaire (attached to this IRB application as "Pre-Assignment Questionnaire") asking about her health, sleep habits, and daily life activities (approximately 30-45 minutes). Participants will receive reminder emails to complete the Questionnaire.

After completing the Pre-Assignment questionnaire, participants will advance to the Sleep Diary phase. Participants will record their sleep online by entering Sleep Diaries (2 minutes to complete each) during the next two weeks. Participants must complete at least 10 diaries in those two weeks to complete this

phase with success. Participants will receive daily email reminders to complete the Sleep Diaries. A sample Sleep Diary is attached to this IRB application as "SHUTi Sleep Diary".

After a participant has completed both the Pre-Assignment Questionnaire and 10 Sleep Diaries in a two-week time period, the program automatically advances the participant to the treatment phase. Via email, participants will be directed to 1 of the 3 study programs to which they have been randomly assigned. For the next nine (9) weeks, each participant will use her assigned study website.

### *Sleep Education/Sleep Hygiene*

One program, patient education, will be a commonly used treatment for insomnia, called sleep information or sleep hygiene. Participants assigned to this treatment program will use a website that discusses ways to improve behaviors and environments that can affect sleep. This material is also included in the other 2 treatments but is presented in a different way. Participants may log in as often as they like and there are no time requirements. An example of this program is attached to this IRB application as "Draft - Sleep Education Website".

### *SHUTi (Sleep Healthy Using the Internet)*

The other 2 treatment programs, Sleep Healthy Using the Internet (SHUTi), and a modification of SHUTi designed for Black women called SHUTi-BWHS, will involve participation in online treatment programs that have six modules called Cores. Each participant will log in to the six modules of her assigned treatment program over a 6 to 8-week period. Participants will use a website program designed to provide tailored instructions about how to improve their sleep. Cores are completed one at a time in order. Each Core is expected to take 45 to 60 minutes to complete. Each Core contains information and exercises designed to help change behaviors and thoughts that can contribute to sleep problems. Participants will receive automated emails encouraging them to complete tasks. Participants will be asked to complete weekly to dos and enter daily Sleep Diaries to track their sleep. After each module, participants will need to complete 5 sleep diaries to proceed to the next module (2 minutes to complete each).

Nine weeks after she completes the initial (Pre-Assignment) questionnaire, regardless of which treatment program she is assigned to, the participant will be asked to complete a Post-Assignment questionnaire about her sleep and health (45 minutes) and she will be asked again to complete 10 sleep diaries. The Post-Assignment Questionnaire will include the same questions asked at the beginning and additional evaluation questions. Six months later, participants will be asked again to complete a questionnaire, including evaluation questions, (45 minutes) and 10 sleep diaries. These three questionnaires are attached to this IRB application as Pre-Assignment Questionnaire, Post-Assignment Questionnaire and 6 Month Follow-up Questionnaire.

Participants can continue to use their assigned website between the two post treatment questionnaires.

After participants have finished their assigned program for the research, they may choose to take one of the other insomnia treatment programs. It will be offered free of charge but it will not be counted as part of this research.

The SHUTi program has 6 cores that include behavioral, educational, and cognitive components. Most cores contain "vignettes" or stories about the sleep problems of specific (fictional) individuals, that may be presented in videos or written material with the names and faces of a variety of (fictional) men and women, of whom one is a Black woman. Some of the cores contain advice from sleep experts (mostly actors playing those roles). This will be revised to make SHUTi-BWHS with the advice of the stakeholder team.

Core 1 provides an overview and rationale for the treatment.

Cores 2 and 3 are behavioral cores that provide rules for sleep restriction and stimulus control. Rules are provided to regulate the sleep-wake schedule and strengthen the connection between the bedroom and sleep. Stimulus control means going to bed only when sleepy, getting out of bed when unable to sleep and returning to bed when sleepy, and curtailing other activities in the bedroom (e.g., reading, television). Sleep restriction means limiting the time spent in bed to increase sleep efficiency (amount of time in bed spent sleeping).

Core 4 focuses on improving sleep hygiene practices (e.g., avoiding alcohol before bedtime).

Core 5, the cognitive core, addresses unhelpful beliefs about sleep (e.g., the belief that a certain number of hours of sleep are required).

Core 6, the last core, integrates the various elements and presents strategies to prevent relapse.

SHUTi-BWHS will have the same structure and elements as SHUTi. The vignettes will be changed, so that Black women will be the characters of interest. The vignettes will also contain material that was not covered in SHUTi, such as sleep problems resulting from housing that is not quiet or that may require room sharing. The "experts" will be Black physicians. . The changes will be made with the advice of a stakeholder team that includes Black women from the community who have sleep problems, a Black community advocate, a sleep expert, a physician who treats individuals with sleep problems, and the co-PIs of this study.

This table summarizes by study week what will happen in this randomized trial.

Step	Week	Study Phase	What happens during this phase	Time required
1	1-2	Pre assignment	Complete Pre- Assignment Questionnaire  Enter 10 sleep diaries in 14 days	30 minutes  2 minutes each
2	3-12	Treatment 9 weeks	Use assigned website	
3	12	Post treatment	Complete Post-Assignment Questionnaire  Enter 10 sleep diaries in 14 days	45 minutes  2 minutes each

4	38	6 months after post treatment	Complete 6 Month Follow-up Questionnaire  Enter 10 sleep diaries in 14 days	45 minutes  2 minutes each
---	----	-------------------------------	---	----------------------------------

## 10 Assessment of Safety and Data Safety Monitoring Plan (DSMP)

### 10.1 Definitions

The following definitions will be used in the assessment of safety:

*Adverse Event (AE)* is any untoward or unfavorable medical occurrence in a human subject, including any abnormal sign (for example, abnormal physical exam or laboratory finding), symptom, or disease, temporally associated with the subject's participation in the research, whether or not considered related to the subject's participation in the research.

*Serious Adverse Event (SAE)* is any adverse event that

- (1) results in death;
- (2) is life-threatening;
- (3) results in inpatient hospitalization or prolongation of existing hospitalization;
- (4) results in a persistent or significant disability/incapacity;
- (5) results in a congenital anomaly/birth defect; or
- (6) based upon appropriate medical judgment, may jeopardize the subject's health and may require medical or surgical intervention to prevent one of the other outcomes listed in this definition (examples of such events include allergic bronchospasm requiring intensive treatment in the emergency room or at home, blood dyscrasias or convulsions that do not result in inpatient hospitalization, or the development of drug dependency or drug abuse).

*Life-threatening* means that the event places the subject at immediate risk of death from the event as it occurred.

*Unanticipated Problem* is defined as an event, experience or outcome that meets **all three** of the following criteria:

- is unexpected; AND
- is related or possibly related to participation in the research; AND
- suggests that the research places subjects or others at a greater risk of harm (including physical, psychological, economic, or social harm) than was previously known or recognized.

*Possibly related* means there is a reasonable possibility that the incident, experience, or outcome may have been caused by the procedures involved in the research

*Unexpected* means the nature, severity, or frequency of the event is not consistent with either:

- the known or foreseeable risk of adverse events associated with the procedures involved in the research that are described in (a) the protocol-related documents, such as the IRB-approved research protocol, any applicable investigator brochure, and the current IRB-approved informed consent document, and (b) other relevant sources of information, such as product labeling and package inserts; or

- the expected natural progression of any underlying disease, disorder, or condition of the subject(s) experiencing the adverse event and the subject's predisposing risk factor profile for the adverse event.

## 10.2 Reporting Plans

The Principal Investigator at BU Medical Campus will report Unanticipated Problems, safety monitors' reports, and Adverse Events to the BMC/BU Medical Center IRB in accordance with IRB policies:

- Unanticipated Problems occurring at BMC/BU Medical Campus involving a fatal or life-threatening event will be reported to the IRB within 2 days of the investigator learning of the event.
- Unanticipated Problems occurring at BMC/BU Medical Campus not involving a fatal or life-threatening event will be reported to the IRB within 7 days of the investigator learning of the event.
- Reports from safety monitors with recommended changes will be reported to the IRB within 7 days of the investigator receiving the report.
- Adverse Events (including Serious Adverse Events) will be reported in summary at the time of continuing review, along with a statement that the pattern of adverse events, in total, does not suggest that the research places subjects or others at a greater risk of harm than was previously known.
- Reports from safety monitors with no recommended changes will be reported to the IRB at the time of continuing review.

## 10.3 Stopping Rules

The study has no stopping rules.

# 11 Data Handling and Record Keeping

## 11.1 Confidentiality

Study data/results, documents, CRFs, and other documents/files will be identified with a unique study ID #. The study ID # will be linked to a master-code list that contains all study ID #s and direct subject identifiers (i.e. name, address, DOB, MRN, etc.). The master-code list will be maintained separately from study files and access limited to the researchers.

Study data, documents, CRFs, and other documents/files for subjects who have been assigned a study ID # will NOT contain any subject identifiers that by themselves or when combined with others identifiers, could result in identifying a subject.

The only identifiable data stored in the SHUTi program will be the participant's email. The assignment into the treatment group in this randomized trial will be done by the BU study coordinator. The email address will be entered into the program by the BU study coordinator. The email will be used to send reminders to the participant of the various phases of the trial; messages will be sent by the SHUTi program at the University of Virginia in an automated fashion. The only identifying information stored in the SHUTi application is the email address. No other identifiable data will be shared or input into the SHUTi program. No identifiable data will be shared with the analyst.

## 11.2 Study Records Retention

Study records will be maintained until seven years post completion of this insomnia treatment study. University of Virginia will destroy emails at the end of the trial.

## 12 Statistical Plan

### 12.1 Sample Size Determination

Power calculations will be based on the data collected from a prior SHUTi trial which included a subset of Black women. The study will be powered at 80% to detect pre-post differences between groups with  $\alpha=.01$ , a recruitment sample size of 303 (n=101 for each randomization group) was targeted. We conservatively estimated 28% study attrition based on prior SHUTi trials, for an anticipated final analytic sample of n=72 for each of the two randomization groups.

### 12.2 Statistical Methods

The chief outcome of interest will be improvement in the ISI score. An ISI score reduction of 8 is considered to be a clinically significant improvement in insomnia symptoms. Other outcomes of interest will be WASO (wake after sleep onset, i.e., amount of time awake after first falling asleep) and SOL (sleep onset latency, i.e., time awake before first falling asleep).

We will analyze the data on an intention to treat basis.

For the primary outcome, ISI, a factorial 2 (groups) x 3 (times) mixed model analysis will compare improvement in the treatment groups to the usual care group, and to one another. Using a General Linear Mixed Model (GLMM) analysis will allow us to include dropouts in the analysis and to model the appropriate temporal dependencies in the dataset.

Analyses for WASO and SOL will be similar.

Finally, an important variable will be the proportion of women who complete SHUTi or SHUTi-BWHS.

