## 4 Objectives

### 4.1 Study Objectives

The goal of this study is to conduct a comparative effectiveness randomized trial of three internet-based intervention approaches to insomnia treatment to assess which of these insomnia interventions are most effective:

- 1) patient education (usual care) (website providing sleep hygiene information)
- 2) standard SHUTi six-module program
- 3) modified SHUTi six-module program tailored for Black women, i.e., SHUTi-BW

We will develop the modified SHUTi program, SHUTi-BWHS with the aid of a stakeholder group that includes Black women, a sleep physician who treats patients with sleep problems at a hospital that serves large numbers of minority patients, sleep experts, and leaders of the randomized trial. Each member of the group will work through the SHUTi cores and be interviewed after each core for suggestions on how to make the program more relevant to Black women. Based on the consensus of the stakeholder group, SHUTi will be modified to with specific sleep problems of Black women in mind.

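### Section 12.2 models baseline ISI as one of three times without saying how it is handled; one shared baseline mean would usually give more precise contrasts at no cost

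*Combined protocol and SAP*

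**What the plan says.** Section 12.2 opens the primary analysis with "For the primary outcome, ISI, a factorial 2 (groups" and continues with "3 (times) mixed model analysis will compare improvement in the treatment groups". It does not list the three times. Section 9 describes exactly three questionnaires: before assignment, at nine weeks, and six months after that. Of the second it says "The Post-Assignment Questionnaire will include the same questions asked at the beginning and additional evaluation questions". Baseline ISI is therefore one of the three modelled times. Section 12.1 is consistent with this, since it states power for pre-to-post differences between groups. WASO and SOL are to be analysed in a similar way.

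No section mentions a baseline covariate, a common baseline mean or a covariance structure.

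Two nearby statements bear on the remedy:

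- **Number of groups.** Section 12.2 specifies two groups, while section 4.1 describes a "comparative effectiveness randomized trial of three internet-based intervention approaches to insomnia treatment" and 12.2 itself compares each SHUTi programme with usual care and with the other.
- **Timing of randomisation.** Section 9 says "After a participant has completed both the Pre-Assignment Questionnaire and 10 Sleep Diaries in a two-week time period, the program automatically advances" the woman to treatment, and that "participants will be directed to 1 of the 3 study programs to which they have been randomly assigned". The same section places enrolment before the baseline questionnaire: "the BWHS Project Coordinator will enroll participants by entering their email and study ID into the SHUTi Administrative site". Section 11.1 adds "The assignment into the treatment group in this randomized trial will be done by the BU study coordinator". The moment of randomisation is not given.

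**The concern.** Section 12.2 does not give the parameterisation, so this step is an inference. A factorial group-by-time model normally includes both main effects and their interaction, which gives each arm its own baseline mean. Improvement is then compared as a difference in mean change, and chance imbalance at baseline passes into the contrast more than it need.

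Randomisation makes the true baseline means equal, and women are directed to their programme only after baseline is complete. Separate baseline means are therefore not needed, and estimating them generally costs precision. This affects all three pairwise ISI contrasts, and WASO and SOL by extension. It is a question of efficiency and of fixing the model in advance; no bias or error-rate problem is involved. Precision matters here because the plan works at alpha .01 with 80% power and 28% expected attrition, and it compares two SHUTi programmes that share the same structure.

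**Working it through.** **Inputs from section 12.1.** 101 women per arm, 28% attrition, 72 per arm analysed, 80% power, alpha .01. The attrition arithmetic holds: 101 × 0.72 = 72.7, stated as 72. The 80% power cannot be reproduced, because no effect size, SD, correlation or sidedness is given. Back-solving at two-sided .01 with 72 per arm gives about 0.58 SD of the analysed quantity (0.576, noncentral t).

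**Assumed inputs.** Let ρ be the correlation between baseline and follow-up, and k the baseline SD divided by the follow-up SD. Neither is in the protocol. I take ρ = 0.3, 0.5, 0.7 and k = 1.0, 0.8, 0.6. All 101 women per arm have a baseline, dropout is ignorable, and the arms share one covariance matrix.

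**Formulas.** Per-arm variance at one follow-up visit, in follow-up SD units:

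- separate baseline means: (1 − ρ²)/72 + (ρ − k)²/101
- shared baseline mean: (1 − ρ²)/72

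The difference, (ρ − k)²/101, is never negative and is zero only when ρ = k.

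**Example, k = 1.0 and ρ = 0.5.** Separate: 0.75/72 + 0.25/101 = 0.01042 + 0.00248 = 0.01289. Shared: 0.01042. The ratio is 0.808, a cut of 19.2%. The standard error of a pairwise contrast falls from √(2 × 0.01289) = 0.161 to √(2 × 0.01042) = 0.144.

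**Full range.** Power is for a contrast that has exactly 80% with separate baselines (two-sided .01, d = 0.576/√(1 − cut), 72 per arm). Extra women per arm = 101/(1 − cut) − 101. Shift is the movement of the separate-baseline contrast, relative to the shared one, for a one-standard-error baseline imbalance: |ρ − k| × √(2/101), in follow-up SD.

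| k | ρ | Variance cut | Power | Extra women per arm | Shift |
|---|---|---|---|---|---|
| 1.0 | 0.3 | 27.7% | 92.6% | 38.8 | 0.10 |
| 1.0 | 0.5 | 19.2% | 89.0% | 24.0 | 0.07 |
| 1.0 | 0.7 | 11.2% | 85.3% | 12.7 | 0.04 |
| 0.8 | 0.3 | 16.4% | 87.7% | 19.8 | 0.07 |
| 0.8 | 0.5 | 7.9% | 83.8% | 8.6 | 0.04 |
| 0.8 | 0.7 | 1.4% | 80.7% | 1.4 | 0.01 |
| 0.6 | 0.3 | 6.6% | 83.1% | 7.1 | 0.04 |
| 0.6 | 0.5 | 0.9% | 80.5% | 1.0 | 0.01 |
| 0.6 | 0.7 | 1.4% | 80.7% | 1.4 | 0.01 (sign reversed) |

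A generalised least squares calculation with three times, and 72 complete and 29 baseline-only women per arm, gives the same variance cuts for all three pairwise contrasts at both follow-ups. Two-arm models also give them, so the gain does not depend on how the two-group wording is read.

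**Where the shared mean could lose.** Suppose the baseline-to-follow-up slopes differ by arm (1.0, 1.0, 0.4), k = 0.6, the follow-up SD is 1 in each arm, and one covariance is pooled over arms. The pooled slope is 0.8. With complete data:

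- Arms 1 v 2, per-arm variance × n: separate 1 − 0.36 = 0.64; shared 0.64 + (0.2)² × 0.36 = 0.6544. Variance rises 2.25%.
- Arms 1 v 3, sum over the two arms: separate 0.64 + 0.9424 + (0.6)² × 0.36 = 1.7120; shared 0.6544 + 0.9424 + (0.4)² × 0.36 = 1.6544. Variance falls 3.36%, and 2 v 3 is the same.

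At 101/72 the figures are +1.59% and −2.42%. With a covariance that differs by arm they become 0.0% and −3.7%, so the loss disappears.

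**The case against.** The best case for leaving the plan alone is that nothing in it is wrong. The planned contrast is unbiased, and 12.1 is written for the same pre-to-post contrast, so no stated power target is missed. The separate baseline means are inferred, and 12.2 does not exclude a shared one. The gain cannot be pinned down: women are selected on a 2015 ISI of 15 or more, which may narrow the baseline spread and lower k, and at k = 0.6 the benefit is worth only 1 to 7 women per arm. One contrast could even lose slightly. The two-group wording and the timing of randomisation are separate defects, and section 9 already implies that women learn their programme after baseline. Baseline ISI as a covariate would also be a reasonable remedy.

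Most of this stands as a limit on size: there is no bias, the gain may be near zero, and the magnitude for WASO and SOL is unknown. It does not remove the point. Baseline handling is unspecified for the primary outcome, and under a common covariance the shared mean cannot do worse in large samples. The possible loss was about 2% in an extreme example, while the other two contrasts gained. The side issues add no weight to the precision argument, but the same sentences have to settle them.

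**Conclusion.** The concern holds. Baseline ISI is one of the modelled times, its handling is not stated, and the usual factorial reading gives valid contrasts that are generally less precise than a shared baseline mean would give. Across the assumed range the variance cut runs from about 1% to 28%, equivalent to about 1 to 39 extra women per arm, with zero gain when ρ = k. These figures are for one pairwise contrast at one visit, and rest on 101 baselines and 72 follow-ups per arm, ignorable dropout and a common covariance. The small gains are plausible given how women are selected, and the protocol does not settle where in the range the trial lies. The change is worth making because it costs almost nothing and fixes the primary model in advance.

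**What to change.** In section 12.2, replace the model description with wording such as:

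> ISI at baseline, post-treatment and 6 months will be analysed in one linear mixed model for all three randomised arms, with one shared baseline mean, free arm-by-time means at both follow-ups and an unstructured covariance; all three pairwise contrasts come from this model. A sensitivity analysis will let the covariance differ by arm. WASO and SOL will be analysed in the same form, with their own baseline diary means.

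This replaces the two-group wording. Women with baseline data only stay in the model, in line with the plan's aim of including dropouts. In section 9, state when randomisation takes place and that women do not learn their assignment until the baseline questionnaire and diaries are complete.

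The cost is three sentences in 12.2 and one in section 9. No new data are needed, and sample size and alpha do not change.
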